C.4.1.2. Baseline Assessment. Dual users who meet inclusion criteria and provide initial verbal consent over the telephone will be sent a bound set of baseline questionnaires or an email link to our survey site. The following questionnaires will be included: (1) a demographic and tobacco history questionnaire including the Fagerström Test for Nicotine Dependence (Heatherton et al., 1991), as well as use of pharmacotherapy and other cessation aids; (2) a questionnaire assessing current and past e-cigarette use that we developed for our recent e-cigarette survey; (3) a continuous measure of readiness to quit, the Contemplation Ladder (Biener & Abrams, 1991); (4) the Stages of Change Algorithm (SOC) (DiClemente et al., 1991); and (5) intentions to quit cigarettes and e-cigarettes. We will also assess three other motivation- related constructs: a situation-specific abstinence self-efficacy scale (Velicer et al., 1990); a recent measure of Abstinence-Related Motivational Engagement (ARME; Simmons et al., 2010), which assesses change in cessation motivation; and a measure of cigarette vs. e-cigarette outcome expectancies that we also developed for our recent survey. To test motivational mechanisms of action, these measures of motivation will be examined as potential moderator variables, with follow-up measures tested as mediators of treatment effects. Finally, we will use 1-item questions to assess overall "commitment" to, and "confidence" about being smoke-free, and 2 questions to assess craving for cigarette smoking.

Inclusion criteria will be evaluated using responses to baseline survey items. Given that participants provided responses during the initial telephone contact that met the inclusion criteria, we created rules for 4 of the 5 inclusion criteria that required strong evidence from the baseline survey for exclusion. The rules acknowledge that participants may mark unintended responses.

Those with the following responses will be excluded based on **Criterion #1** (smoking \geq 1 tobacco cigarette/week over the past year).

- Rule 1) Marked either '1-5 days a month' or 'No use in the past month' to item 4 in the 'Tobacco Cigarettes' section.
- Rule 2) Marked the designated answer to any two or more of the following in the 'Tobacco Cigarette' section: a) Item 4a: response of 7 or more days since last cigarette;
 - b) Item 5: response of 'no use in the past month'; c) Item 7: response of 'I do not smoke';

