The primary statistical analyses will assess the effectiveness of the full intervention (eTARGET) in producing smoking cessation compared to the no-treatment control (ASSESS) and the generic smoking cessation booklets(GENERIC). Based on prior published work ([name] et al., 2013), data from our cessation study (C.1.2.3), and considering that the sample will not be limited to treatment-seekers, we estimate no greater than 15% abstinence by 18 months in ASSESS, with at least 5% increments for GENERIC and eTARGET, respectively. We estimated sample size using GEESIZE version 3.1 (Rochon, 2003) with an AR(1) working correlation structure and coefficient of 0.7; adjusted alphas of .017 (ASSESS vs. eTARGET), .025 (ASSESS vs. GENERIC), and .05 (GENERIC vs. eTARGET) following Holm's procedure (Holm, 1979); and abstinence rates that increase from 6 to 18 months, then remain stable through 30 months. Randomizing 2065 participants based on 1:2:2 relative sizes (413 to ASSESS; 826 to GENERIC, and 826 to eTARGET) ensures ≥80% power for all contrasts. We plan to recruit 580, 1160, and 1160 individuals, respectively, in expectation of 17% attrition after baseline assessment, as observed in our prior study.

We initially planned to recruit 500, 1000, and 1000 individuals, respectively, in expectation of 17% attrition after baseline assessment, as observed in our prior study. Based on return rates of the 3-month survey for the first 575 study participants, we now expect 27.5% attrition after baseline. Therefore, we plan to recruit 2900 individuals (400 more than initially planned) with 580, 1160, and 1160 individuals in the ASSESS, GENERIC, and eTARGET conditions, respectively. This will ensure the same sample size for statistical analysis at the higher-than-expected attrition rate.

C.6.3. Data Analysis Overview

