Participants will be randomized into the three conditions using balanced-permuted block randomization with a block size of 10 (2-4-4). Analyses will be conducted with SAS version 9.3 and Mplus Version 7 (Muthén & Muthén, 2008). Frequency distributions and contingency table analyses will be used as a point of departure for more advanced analyses. Multiplicity will be legitimately adjusted as needed for Aim 2, but not for the secondary or exploratory analyses. We will perform attrition analyses, using survival analysis, to test whether the attrition rate differs across intervention arms, if participants and dropouts differ on key variables, and if such variables moderate attrition differences across arms. The median time to attrition and its 95% confidence interval, will be summarized by intervention arm using the Kaplan-Meier method with log-rank test. Any significant variables on those attrition patterns in multivariable Cox Proportional Hazards (PH) models will be accounted for during multiple imputations as well as in the main analysis.

To manage missing data, multiple imputation under the Missing at Random assumption will be applied using a Markov Chain Monte Carlo method (Shafer, 1997) via PROC MI in SAS, given the expected large number of non-monotonic missing data patterns. Preliminary analyses will determine auxiliary variables (e.g., baseline measures that predict smoking status at follow-up) to be used. A post hoc approach (Rubin, 1987) will address the influence of Missing Not at Random (MNAR) on smoking status (i.e., missing is due to smoking). Sensitivity analyses will be performed to assess alternative multiple imputation techniques upon the extent of MNAR influences.

C.6.4. Analytic Plan for Addressing Specific Aims.

C.6.4.1. Specific Aim 1 (see C.2.3.2.) and Aim 3 (see C.5.)

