C.6.4.2. Specific Aim 2. Generalized estimating equations (GEE) will be used to fit populationaveraged models to handle the longitudinally measured binary outcomes, with the main covariates of intervention conditions, time (months from baseline), and the interaction of condition and time. Potential confounding variables (e.g., group differences in demographic, smoking history, or pharmacotherapy use) that appear despite randomization will be adjusted for in the model. Pair-wise condition and time interval comparisons will be tested using the generalized score statistics from GEE models by utilizing the contrast statements. Further, the generalized linear mixed effects models with a logit link function will be expanded, including the participant-specific intercept and slopes as the random effects in the model. Moderators (e.g., gender, SES, quitting motivation, nicotine dependence, magnitude of e-cigarette use, expectancies)will be tested via interactions with condition and condition x time. *Mechanisms of change associated with treatment*

will be tested (e.g., motivational measures, intervention usage, e-cigarette usage) via mediation analysis, performed using Hayes' (2009) "Indirect" macro within SAS. The approach described above will be used to evaluate the primary outcome of smoking cessation as well as the secondary outcome of e-cigarette cessation.

We will extend our analysis to lapse/recovery models using the Kaplan-Meier method with log-rank test for the stratified sub-groups (e.g., lapsed and recovered groups) to test the effect of intervention condition and Cox PH models controlling potential confounding variables.

To capture proportional shifts in cigarette vs. e-cigarette use, we will create a response variable with multiple levels for each follow-up assessment reflecting the relative level of e-cigarette to cigarette use, referenced against baseline use of each product. The multi-level outcome variable will be fitted using a logistic analysis on the generalized logits to test if the interventions have a significant impact on these shifts.

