C.6.4.3. Secondary Aim. This aim is to describe the patterns of cigarette smoking and ecigarette use among initial dual users at 3-month intervals for 2 years. This process will occur relatively naturalistically in the ASSESS condition. The primary analysis will be completed using a growth mixture model (Ram & Grimm, 2009) applied via Mplus Version 7. Growth mixture models assume each participant has his/her own trajectory of smoking cessation behavior over time. We aim to (1) describe the trajectories for tobacco cigarette and e- cigarette use, and (2) identify distinct subgroups of trajectories over time. The model assessment will be conducted using residuals for the fitted means or covariance, as well as overall model fit indices.

C.7. Study Design Considerations

C.7.1. Should we recruit only treatment seekers? Limiting recruitment to treatment-seeking (or cessation-motivated) dual users would parallel most conventional intervention trials. However, we decided to recruit dual users more generally into the broader surveillance study (Secondary Aim), but inform them of the treatment arms before obtaining consent. Not only are most dual users cessation-motivated, but other advantages of this approach include: (1) We will be able to test whether our intervention motivates attempts to quit smoking among non-treatment-seeking, non-cessation-motivated dual users. (2) We will be able to test cessation-motivation (Contemplation Ladder) as a moderator variable. (3) A broad recruitment strategy models likely dissemination approaches for a low-cost self-help intervention (i.e., external validity). (4) We avoid appearing to promote e-cigarette as a cessation tool for current smokers (see C.7.3). (5) We increase the generalizability of the surveillance study of the Secondary Aim.

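### The primary GEE guarantees no prognostic baseline covariate: covariates enter only through chance imbalance or significance in attrition models, so modest precision on the two 5-point contrasts may be lost

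*Combined protocol and SAP*

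**What the plan says.** C.6.4.2 specifies a GEE with condition, time and condition by time. It then adds covariates conditionally: "Potential confounding variables (e.g., group differences in demographic, smoking history, or pharmacotherapy use) that appear despite randomization will be adjusted for in the model". No test, threshold or closed list is given.

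C.6.3 opens a second route. Variables significant in multivariable Cox models of attrition "will be accounted for during multiple imputations as well as in the main analysis". No significance level is given. Randomisation is in permuted blocks of 10 with no stratification factor stated, so the design brings in no covariate either.

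Baseline measures that could predict abstinence are collected (C.4.1.2: dependence, Contemplation Ladder, tobacco and e-cigarette history), but the plan gives them other uses:
- Imputation auxiliaries (C.6.3): "Preliminary analyses will determine auxiliary variables (e.g., baseline measures that predict smoking status at follow-up) to be used".
- Moderators (C.6.4.2): "Moderators (e.g., gender, SES, quitting motivation, nicotine dependence, magnitude of e-cigarette use, expectancies)will be tested via interactions". Likewise C.4.1.2, "these measures of motivation will be examined as potential moderator variables", and C.7.1, "We will be able to test cessation-motivation (Contemplation Ladder) as a moderator variable".

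C.4.2 says results will be reported under both multiple imputation and intent-to-treat.

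**The concern.** In a randomised trial the reason to adjust for a baseline covariate is that it predicts the outcome. An observed imbalance between randomised arms is chance, and a variable that predicts dropout need not predict abstinence. A rule built on those two triggers can leave out a strong predictor that happens to be balanced and unrelated to dropout.

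Two things are at stake. The first is precision on ASSESS vs GENERIC and GENERIC vs eTARGET, each planned at a 5-point difference. The second is that the covariate set is unknown until dropout has been observed. With a logit link, adding covariates makes the odds ratio conditional on them, so a set chosen from the data also leaves open exactly which odds ratio the trial will report.

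**Working it through.** **Inputs from C.6.2.** Abstinence at 18 months of 15/20/25%; alphas of .017 (ASSESS vs eTARGET), .025 (ASSESS vs GENERIC) and .05 (GENERIC vs eTARGET), taken as two-sided because sidedness is not stated; 413/826/826 analysed; AR(1) correlation 0.7; 580/1160/1160 recruited; and "we now expect 27.5% attrition after baseline".

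**Inputs assumed, not in the documents.** The share of outcome variance explained by the baseline covariates (R²), and how strongly the same covariates predict dropout (hazard ratio, HR, per SD).

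**Step 1. The plan's own figure.** C.6.2 states at least 80% power for every contrast. This cannot be reproduced exactly, because the 6- and 12-month rates, the visits used and the tested contrast are not given. At 18 months alone, power is 96.1% (ASSESS vs eTARGET), 46.0% (ASSESS vs GENERIC) and 68.2% (GENERIC vs eTARGET), so the claim relies on the repeated measures. A visit-averaged GEE contrast with ASSESS at 5/10/15/15/15% over 6 to 30 months and constant 5-point steps gives 99.9/80.2/91.9%. The claim is reachable under some trajectories. Attrition is consistent: 2065/0.725 = 2849, against 2900 planned.

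**Step 2. Fixed adjustment against no adjustment, from 80% power.** Adjustment multiplies the variance by about (1 − R²), so power = Φ[(z₀.₈₀ + z₁₋α/₂)/√(1 − R²) − z₁₋α/₂].
- α = .05, R² = 5%: 2.802/0.9747 − 1.960 = 0.915, giving 82.0%. R² = 10%: 2.802/0.9487 − 1.960 = 0.994, giving 84.0%.
- α = .025, R² = 5%: 3.083/0.9747 − 2.241 = 0.922, giving 82.2%. R² = 10%: 3.083/0.9487 − 2.241 = 1.009, giving 84.3%.

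The gain is about 2 points at R² 5% and 4 points at 10%.

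**Step 3. How often the two routes already admit a covariate.** Dropouts: 0.275 × 2900 ≈ 798. The attrition test has expected z ≈ ln(HR) × √798. That is 1.38, 2.69 and 3.95 for HR 1.05, 1.10 and 1.15, so entry at p < .05 (assumed threshold) is about 28, 77 and 98%, and 5% at HR 1.00. Adding a 5% imbalance trigger gives 1 − 0.95 × (1 − entry), or about 10, 32, 78 and 98% for HR 1.00, 1.05, 1.10 and 1.15.

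**Step 4. Fixed list against the two-route rule.** Simulation of three arms with six equally prognostic covariates, 27.5% dropout, logistic Wald tests in completers at one time point, and 6000 trials per row (Monte Carlo SE at most 0.65 points). Power in %, unadjusted / two-route / fixed:

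| HR per SD | R² | GENERIC vs eTARGET | ASSESS vs GENERIC |
|---|---|---|---|
| 1.00 | 5% | 68.7 / 68.9 / 71.2 | 46.5 / 46.8 / 49.3 |
| 1.00 | 10% | 69.3 / 69.6 / 74.0 | 46.2 / 46.9 / 51.4 |
| 1.05 | 5% | 67.8 / 68.4 / 69.8 | 46.0 / 46.5 / 48.2 |
| 1.05 | 10% | 68.3 / 69.6 / 73.5 | 46.2 / 47.4 / 50.5 |
| 1.10 | 5% | 67.9 / 70.2 / 70.8 | 45.8 / 47.0 / 47.8 |
| 1.10 | 10% | 66.6 / 71.0 / 71.8 | 46.0 / 49.1 / 50.3 |

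Fixed minus two-route is 2.3 to 4.5 points at HR 1.00, 1.4 to 3.9 at HR 1.05 and 0.6 to 1.2 at HR 1.10. Over R² of 2.5 to 13%, the HR 1.10 gain is 0.2 to 1.6 points, and 0.2 to 2.1 in a four-visit GEE check (3000 trials). At HR 1.15 it is at most 0.2. ASSESS vs eTARGET gains under 2 points in every case. With missing counted as smoking, at HR 1.10, the gain is under 1 point.

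**Step 5. Null check.** With 20% abstinence in all arms, R² 13% and HR 1.00 and 1.10, the two-route rule rejects in 4.8 and 4.7% (nominal 5), 2.0 and 2.5% (nominal 2.5) and 1.5 and 1.5% (nominal 1.7).

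Multiple imputation and the planned score tests were not simulated.

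**The case against.** Several counter-arguments have force.

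- *The routes are not blind to prognosis.* A confounder must relate to outcome as well as arm, so C.6.4.2 leaves room for judging prognosis. If the intent-to-treat analysis in C.4.2 counts missing as smoking, a predictor of dropout also predicts that outcome. In the earlier cessation trial (Table 1) the intent-to-treat N stays at 1874 with lower rates, which fits that reading. This stands: it would be too strong to say that neither route ever selects prognostic variables. It does not make any of them certain to enter.
- *The larger gains need unlikely conditions.* Gains well above 2 points over the two-route rule need covariates that predict abstinence but have little or no link to dropout, and they were simulated from baselines below the stated 80%. This stands, and the size below is limited accordingly.
- *Auxiliaries already use the information.* They do, but only for missing outcomes.
- *Both rules can be run without seeing abstinence by arm.* True. The first needs only baseline data and the second only dropout.

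A reader might infer that the data-driven rule inflates type I error or biases the comparison. The documents do not show this, and the simulated null rates are at or below nominal. A reader might also infer that the trial is under-sized for want of adjustment, but C.6.2 does not count on adjustment, so no power promise is broken. Finally, pharmacotherapy use in C.6.4.2 might be read as post-randomisation use. Its examples match the first baseline questionnaire in C.4.1.2, so this calls for at most a clarifying word.

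**Conclusion.** The point holds as a modest loss of precision and an unfixed covariate set, not as a threat to validity. From about 80% power on a 5-point contrast, the gain of a fixed set over no adjustment is roughly 2 points at R² 5% and 4 points at R² 10%. Against the rule actually planned, it is about 0 to 2 points if the covariates moderately predict dropout (HR near 1.10 per SD) and near zero if they strongly do (HR 1.15). The 10-point contrast is hardly affected. R², the dropout association and the p < .05 triggers are assumptions. The absolute powers in the simulation are not a check on C.6.2. The change is worth making because the benefit, though small and uncertain, costs almost nothing.

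**What to change.** In C.6.4.2, replace the imbalance trigger with a short list of baseline covariates, settled before outcomes are examined by arm and used regardless of imbalance. Candidates already collected are smoking frequency, nicotine dependence score, Contemplation Ladder, e-cigarette use, sex and SES. Use pre-randomisation values only; writing baseline before pharmacotherapy use is an optional clarification.

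Put the list in both the imputation model and the primary GEE. In C.6.3, keep attrition-selected variables in the imputation model, and show their addition to the outcome model as a labelled sensitivity analysis. Report the unadjusted model alongside.

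The cost is SAP wording, with no new data or visits. The small downside is that the adjusted odds ratio is conditional on the listed covariates, which is why the unadjusted result should sit next to it.

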Participants will be 2900 weekly smokers, recruited throughout the US, with an emphasis on Central Florida (for bioverification; see C.4.1.4) via multimedia advertisements (daily and weekly newspapers, radio, cable TV, social media, e-cigarette forums, etc.). To maximize generalizability, we will have minimal inclusion criteria assessed at the time of the telephone screening: (1) smoking \geq 1 tobacco cigarette/week over the past year; (2) e-cigarettes use \geq 1/week over the past month; (3) age \geq 18 years; (4) not currently enrolled in a face-to-face smoking cessation program; and (5) able to speak and read English. Upon receipt of the baseline, if it is determined that a participant no longer meets the inclusion criteria, they will be withdrawn from the study (see C.4.1.2 for details). At that time, they will be sent a withdrawal letter and provided with a copy of NCI's Clearing the Air booklet.

In addition, to reduce leakage of information about differences in treatment conditions among participants, we will limit the number of participants from the same street address to 1, and not allow more than 2 referrals per participant. We will assess whether participants use any other smoking cessation services (e.g., state quitline, websites) or pharmacotherapy so that we can examine their impacts statistically, but we will not exclude smokers who utilize these widely available smoking cessation tools. Participants will be invited to a study examining tobacco and e-cigarette use over time and told that they may also receive materials to help them quit. That is, we will not limit recruitment to treatment-seeking e-cigarette users. (See C.7.1)

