At each assessment point we will calculate point-prevalence abstinence rates (for tobacco smoking as well as e-cigarette use) using 7-day, 30-day, and 90-day criteria. Point-prevalence measures are best for capturing the dynamic nature of cessation, maintenance, and relapse. The 7-day criterion will serve as our primary outcome index. Continuous abstinence is not feasible because guit dates will be highly variable across participants, and also because one goal of the intervention is to encourage lapsers to guit again (recycle). We need our outcome measures to reflect these changes in smoking status over time. However, the 30-day and 90-day point-prevalence abstinence criteria also reflect more prolonged abstinence than the 7day criterion usually used in treatment studies (Velicer et al., 1992). We will also compare groups on continuous measures, such as current smoking rate (cigarettes/day), months of smoking during the follow-up period, length of current abstinence period, and latency from quit date to relapse. Outcomes will be reported that account for missing follow-up data using both multiple imputation (MI) and intent-to-treat (ITT) approaches.

C.5. Cost-Effectiveness Analysis (Aim 3)

The relative effectiveness and costs of the intervention compared to standard care will be measured based on the health care system perspective. Using the trial endpoint results, effectiveness will be predicted in terms of smoking cessation and translated into life years and quality adjusted life years (QALY) based on published associations between smoking cessation and long-term health outcomes (Cohen & Fowler, 1993; Torrance, 1986). Costs include the intervention costs, collected prospectively, and lifetime costs of reduced medical expenditures attributable to smoking cessation, that will be modeled using published estimates (e.g., Berman et al., 2013; Cowan & Schwab, 2011; Fishman et al., 2003; Hockenberry et al., 2012; Hodgson, 1992; Oster et al., 1984). No out-of-pocket costs or transfer payments (i.e., increased social security due to longevity) will be incorporated into the analysis, because they do not fall within the system perspective. In addition, costs associated only with research (e.g., mailing of assessments) will be excluded. Monetary values will be inflation adjusted, and all outcomes will be presented in discounted and undiscounted values.

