C.7.2. Printed versus internet-based materials. In theory, an internet-based intervention offers some substantial advantages: no printing or mailing costs; constant availability; and ease of distribution. However, there are also some advantages of traditional printed materials: potentially greater salience and retrievability of a tangible product: use and portability not dependent on technology; and less affected by economic barriers that may limit internet access. Because our previous efficacy studies that produced strong findings used printed materials, we are hesitant to make a wholesale shift to internet-based content. Doing so would impair our ability to interpret a failure to replicate the previous results. However, we recognize the potential advantages of internet-based delivery of health promotion content. Therefore, for the proposed study we will offer participants the option of also receiving an email with a personalized link to the appropriate booklet and to all earlier booklets in the series. They will receive this email an average of 2-3 days before they receive the printed booklets by US mail. We will collect metadata regarding use of the internet-based documents, namely how many times the link was accessed, and whether the electronic booklet(s) were downloaded, which will allow us to document their use and acceptability. We will also collect evaluations and preferences regarding internet distribution at follow-up to test as potential moderators or mediators of treatment effects. This information should assist us in deciding whether to transition fully to internet-based or mobile content (i.e., smart-phone/tablet apps) distribution in the future.

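### The lapse/recovery tests and the quit-to-relapse latency compare arms within groups formed after randomisation, so they are not randomised comparisons and can show a false effect or hide a real one

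*Combined protocol and SAP*

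**What the plan says.** Three places in the combined protocol and SAP bear on this.

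- **C.6.4.2 (Specific Aim 2).** After the GEE and mixed models, the plan adds lapse/recovery models. Log-rank tests are used "for the stratified sub-groups (e.g., lapsed and recovered groups) to test the effect of intervention condition", and these are supplemented by "Cox PH models controlling potential confounding variables". The covariates are not named. Lapse, recovery, the time origin and the event are not defined.
- **C.4.2 (Outcome Variables).** Among the continuous measures on which the arms are compared are "length of current abstinence period, and latency from quit date to relapse".
- **C.7.2 (Printed versus internet-based materials).** The plan will collect evaluations and "preferences regarding internet distribution at follow-up to test as potential moderators or mediators of treatment effects".

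On who can be in these groups, C.3.2 states: "Participants will be 2900 weekly smokers". C.6.3 randomises them 1:2:2 in blocks of 10, with no stratification factor named. C.4.2 adds that "one goal of the intervention is to encourage lapsers to guit again".

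**The concern.** Having a quit date, having lapsed and having recovered are all consequences of what happens after allocation. If the booklets bring less-ready smokers to a quit attempt, which C.7.1 lists as something the trial will test, then eTARGET quitters include people whose counterparts in ASSESS never quit. A log-rank test among quitters or lapsers then compares different kinds of people as well as different booklets.

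An intervention that succeeds in producing quits could appear to cause relapse, or a real relapse-prevention effect could be cancelled out. The plan words the analysis as a test of the effect of condition under the main efficacy aim, and nothing marks it as non-randomised.

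**Working it through.** **1. Are the groups fixed at randomisation?** No. All participants smoke at entry (C.3.2), and the baseline rules in C.4.1.2 exclude those who turn out not to. A lapse needs a quit after randomisation, and a recovery needs a lapse after that. Reading lapse and recovery as events rather than strata does not help: time to lapse exists only after a quit, and time to recovery only after a lapse.

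**2. Is there a figure in the plan to reproduce?** No. C.6.2 covers the GEE abstinence contrasts; the lapse/recovery models have no sample size, event count or power. The size below therefore rests on stated assumptions.

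**3. Formula.** Per 100 randomised, let q quit in any arm and relapse with probability r. Let e more quit only under eTARGET and relapse with probability r + d. The booklets change nobody's relapse risk.

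- ASSESS relapse among quitters = r
- eTARGET relapse among quitters = [q·r + e·(r + d)] / (q + e)
- False difference = e·d / (q + e)

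**4. Inputs.** From C.6.2, planned abstinence at 18 months is 15% in ASSESS, with 5-point steps to 20% in GENERIC and 25% in eTARGET. The gap of 25 − 15 = 10 is used for e, as a stand-in for the gap in ever quitting. Assumed: r = 50% and d = 20 points. The plan does not give q. A value of 15 is a low extreme, because 18-month point-prevalence abstainers are only some of those who ever quit. In the team's own survey (C.1.4, self-selected) 84% of dual users reported a serious quit attempt in the past year. The range shown is 15 to 80.

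| q | eTARGET relapse among quitters | ASSESS | False harm |
|---|---|---|---|
| 15 | (15×0.50 + 10×0.70)/25 = 58.0% | 50% | 8.0 points |
| 40 | (40×0.50 + 10×0.70)/50 = 54.0% | 50% | 4.0 points |
| 60 | (60×0.50 + 10×0.70)/70 = 52.9% | 50% | 2.9 points |
| 80 | (80×0.50 + 10×0.70)/90 = 52.2% | 50% | 2.2 points |

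If e = 0 or d = 0 the difference is zero.

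**5. GENERIC v eTARGET.** With e = 5 for GENERIC and q = 15, GENERIC shows (15×0.50 + 5×0.70)/20 = 55%, against 58% for eTARGET: 3 points.

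**6. Hiding a real effect.** Take q = 40 and let eTARGET truly lower relapse by 4 points in everyone. Observed relapse is (40×0.46 + 10×0.66)/50 = 50%, the same as ASSESS, so the benefit disappears.

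**7. Effect on the test.** A simulation (4,000 trials per setting, arms of 413 and 826) let an unmeasured trait drive both quitting and relapse, with no arm effect on relapse. Quitting was set at 15% v 25%, so it sits at the low-q extreme. Relapse at 12 months was assumed to be about 58% at the average trait value. The log-rank test among quitters, at two-sided 0.05, gave:

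- ASSESS v eTARGET: apparent hazard ratio 1.05 to 1.24, rejection 4.9% to 9.2%, with 77-96% of rejections pointing to harm.
- GENERIC v eTARGET (826 per arm, 20% v 25%): hazard ratio 1.03 to 1.12, rejection 5.1% to 7.9%.
- No shared trait, or equal quit rates: hazard ratio 0.99 to 1.00, rejection 4.4% to 5.5%.

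**The case against.** The strongest reply is that the demonstrated effect is modest and conditional. That stands: the bias needs the arms to differ in who quits and the extra quitters to differ in relapse risk. A reader might infer an 8-point false harm from the plan's own quit rates. The documents do not support that, because 15% and 25% are abstinence at 18 months, not the share who ever quit, and the relapse rates are not the plan's.

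Second, whole-sample outcomes are already planned. C.4.2 lists months of smoking during follow-up and current cigarettes per day, and length of current abstinence can be set to zero for current smokers. This stands too. Among the C.4.2 measures named here, only latency from quit date to relapse clearly requires a quit.

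Third, relapse prevention is a core purpose of these booklets (A.3.1, C.2.2), so dropping every comparison among quitters would lose something of interest. Agreed: labelling is enough.

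Fourth, a reader might infer from C.7.2 that the plan generally uses follow-up measures as moderators. It does not. For the motivation measures, C.4.1.2 tests baseline values as moderators and follow-up values as mediators, and follow-up delivery preferences can properly be mediators. Nor does the lack of materials in ASSESS prevent a GENERIC v eTARGET analysis, since both arms are offered the electronic versions (C.3.3).

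What none of this answers is that the tests in C.6.4.2 are made within groups that treatment is meant to change, with no method to deal with that selection. Unnamed Cox covariates remove at most the measured part.

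**Conclusion.** The concern holds for two items: the within-group tests of condition in C.6.4.2 and the quit-to-relapse latency in C.4.2. Neither is a randomised comparison. Each can mislead in either direction, since extra quitters who relapsed less often would produce a false benefit. The documents do not fix the size. Under the assumed rates it is about 2 to 4 points when 40-80% would quit in any arm and 8 points at the 15% extreme.

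A reader might infer that the trial's main result is compromised. It is not: the GEE analysis of 7-day abstinence compares randomised conditions and does not use these groups. The C.7.2 moderator wording is a minor, separate matter. The change should be made, but it concerns a secondary extension.

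**What to change.** 1. In C.6.4.2, make the arm test for lapse and recovery a from-randomisation analysis in all randomised participants. One option is a multi-state model (smoking, abstinent, lapsed, recovered), contrasting the probability of being in each state over 24 months. Contrasting only the abstinent-to-lapsed transition would bring the same selection back. Another is the already planned months of smoking, with never-quitters counted as smoking throughout.
2. Report comparisons within quitters or lapsers, including latency to relapse, as descriptive secondary results labelled non-randomised.
3. Define lapse, recovery, time origin and event, and name the baseline covariates in advance.
4. In C.7.2, use delivery preferences measured at follow-up as mediators or descriptively, not as moderators.

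The cost is SAP wording and some programming. The three-monthly reports of use in C.4.1.3 already supply the data. The downside is that there is no randomised test of relapse among quitters alone.
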